### **10.1.2 Serious adverse events**

An SAE is defined as any AE (appearance of (or worsening of any pre-existing) undesirable sign(s), symptom(s) or medical condition(s)) which meets any one of the following criteria:

- Fatal

- Life-threatening
  - Life-threatening in the context of a SAE refers to a reaction in which the patient was at risk of death at the time of the reaction; it does not refer to a reaction that hypothetically might have caused death if it were more severe (please refer to the ICH-E2D Guidelines).
- Results in persistent or significant disability/incapacity
- Constitutes a congenital anomaly/birth defect
- Requires inpatient hospitalization or prolongation of existing hospitalization, unless hospitalization is for:
  - Routine treatment or monitoring of the study indication, not associated with any deterioration in condition.
  - Elective or pre-planned treatment for a pre-existing condition that is unrelated to the indication under study and has not worsened since signing the informed consent
  - Social reasons and respite care in the absence of any deterioration in the patient's general condition
  - Treatment on an emergency outpatient basis for an event not fulfilling any of the definitions of a SAE given above and not resulting in hospital admission
- Is medically significant, e.g. defined as an event that jeopardizes the patient or may require medical or surgical intervention to prevent one of the outcomes listed above.

Medical and scientific judgment should be exercised in deciding whether other situations should be considered serious reactions, such as important medical events that might not be immediately life threatening or result in death or hospitalization but might jeopardize the patient or might require intervention to prevent one of the other outcomes listed above. Such events should be considered as “medically significant”. Examples of such events are intensive treatment in an emergency room or at home for allergic bronchospasm, blood dyscrasias or convulsions that do not result in hospitalization or development of dependency or abuse (please refer to the ICH-E2D Guidelines).

In this study, nAMD recurrences and their clinical manifestations are exempt from reporting. Patient treatment is based on disease activity, which is assessed and recorded throughout the study in the eCRF. Moreover, nAMD is a progressive disease while its treatment is a non-continuous drug administration so disease activity might mean that a patient needs more frequent dosing rather than lack of efficacy.

All malignant neoplasms will be assessed as serious under “medically significant” if other seriousness criteria are not met.

Any suspected transmission via a medicinal product of an infectious agent is also considered a serious adverse reaction.

All reports of intentional misuse and abuse of the product are also considered serious adverse event (SAE) irrespective if a clinical event has occurred.

### **10.1.3 SAE reporting**

To ensure patient safety, every SAE, regardless of causality, occurring after the patient has provided informed consent and until the last study visit or 30 days after the last administration of study treatment whichever is later must be reported to Novartis safety immediately, without undue delay, under no circumstances later than within 24 hours of learning of its occurrence. Detailed instructions regarding the submission process and requirements are to be found in the investigator folder provided to each site.

All follow-up information for the SAE including information on complications, progression of the initial SAE and recurrent episodes must be reported as follow-up to the original episode within 24 hours of the investigator receiving the follow-up information. An SAE occurring at a different time interval or otherwise considered completely unrelated to a previously reported one must be reported separately as a new event.

If the SAE is not previously documented in the IB or Package Insert (new occurrence) and is thought to be related to the study treatment, a Chief Medical Office & Patient Safety (CMO & PS) Department associate may urgently require further information from the investigator for health authority reporting. Novartis may need to issue an investigator notification (IN) to inform all investigators involved in any study with the same study treatment that this SAE has been reported.

Suspected unexpected serious adverse reactions (SUSARs) will be collected and submitted to the Competent Authorities and relevant Ethics Committees in accordance with EU Guidance 2011/C 172/01 or as per national regulatory requirements.

Any SAE occurring after the patient has provided informed consent and until the last study visit or 30 days after the last administration of study treatment whichever is later will be reported.

Any SAEs experienced after the above mentioned period should only be reported to Novartis Safety if the investigator suspects a causal relationship to study treatment.

### **10.1.4 Pregnancy reporting**

Women of childbearing potential are excluded from this study.

To ensure patient safety, each pregnancy occurring after signing the informed consent must be reported to Novartis within 24 hours of learning of its occurrence (female participants only).

The pregnancy (for female participants) should be followed up to determine outcome, including spontaneous or voluntary termination, details of the birth, and the presence or absence of any birth defects, congenital abnormalities, or maternal and/or newborn complications.

Pregnancy should be recorded and reported by the investigator to the Novartis CMO & PS Department. Pregnancy follow-up should be recorded on the same form and should include an assessment of the possible relationship to brolocizumab (investigational) with any pregnancy outcome.

Any SAE experienced during pregnancy must be reported.

### 10.1.5 Reporting of study treatment errors including misuse/abuse

Medication errors are unintentional errors in the prescribing, dispensing, administration or monitoring of a medicine while under the control of a healthcare professional, patient or consumer (European Medicines Agency definition).

Study treatment errors and uses outside of what is foreseen in the protocol will be collected in the dose administration record in the eCRF and in the Dispensing Log at the study site, irrespective of whether or not associated with an AE/SAE and reported to Safety only if associated with an SAE.

**Table 10-1 Guidance for capturing the study treatment errors including misuse/abuse**

Treatment error type	Document in Dose Administration (DAR) eCRF (Yes/No)	Document in AE eCRF	Complete SAE form
Unintentional study treatment error	Yes (only date and time of injection)	No	Only if associated with an SAE

For more information on AE and SAE definition and reporting requirements, please see the respective sections ([Section 10.1.1](#), [Section 10.1.2](#) and [Section 10.1.3](#)).

### 10.1.6 Adjudication committee

Not applicable.

## 11 Data collection and database management

### 11.1 Data collection

Designated investigator staff will enter the data required by the protocol into the eCRFs. The eCRFs have been built using fully validated secure web-enabled software that conforms to 21 Code of Federal Regulations (CFR) Part 11 requirements. Investigator site staff will not be given access to the EDC system until they have been trained. Automatic validation programs check for data discrepancies in the eCRFs, allow modification and/or verification of the entered data by the investigator staff.

The investigator/designee is responsible for assuring that the data (entered into eCRF) is complete, accurate, and that entry and updates are performed in a timely manner. The investigator must certify that the data entered are complete and accurate.

After final database lock, the investigator will receive copies of the patient data for archiving at the investigative site.

All data must be recorded, handled and stored in a way that allows its accurate reporting, interpretation and verification.

### 11.2 Database management and quality control

Novartis (or designated CRO) personnel will review the data entered by investigative staff for completeness and accuracy. Electronic data queries stating the nature of the problem and

requesting clarification will be created for discrepancies and missing values and sent to the investigative site via the EDC system. Designated investigator site staff are required to respond promptly to queries and to make any necessary changes to the data.

Concomitant treatments and prior medications entered into the database will be coded using the World Health Organization (WHO) Drug Reference List, which employs the Anatomical Therapeutic Chemical classification system. Medical history/current medical conditions and AEs will be coded using the Medical Dictionary for Regulatory Activities (MedDRA) terminology.

Ocular images will be handled as described in [Section 8.3.1](#) and [Section 8.3.2](#). The Data management staff will review data received from the CRC. Data Review will be done for data structure and data completeness / accuracy as defined in Vendor Data Transfer Specifications.

The occurrence of relevant PDs will be determined at Week 12 before the interim database lock for the primary analysis and at the conclusion of the study. Once all the necessary actions have been completed and the database has been declared to be complete and accurate, it will be locked. Any changes to the database after that time can only be made after written agreement by Novartis development management.

### **11.3 Site monitoring**

Before study initiation, at a site initiation visit or at an investigator's meeting, a Novartis/ designated CRO representative will review the protocol and data capture requirements (i.e. eSource DDE or eCRFs) with the investigators and their staff. During the study, Novartis employs several methods of ensuring protocol and GCP compliance and the quality/integrity of the sites' data. The field monitor will visit the site to check the completeness of patient records, the accuracy of data capture / data entry, the adherence to the protocol and to GCP, the progress of enrollment, and to ensure that study treatment is being stored, dispensed, and accounted for according to specifications. Key study personnel must be available to assist the field monitor during these visits. Continuous remote monitoring of each site's data may be performed by a centralized Novartis/ designated CRO. Additionally, a central analytics organization may analyze data & identify risks & trends for site operational parameters, and provide reports to Novartis clinical teams to assist with trial oversight.

The investigator must maintain source documents for each patient in the study, consisting of case and visit notes (hospital or clinic medical records) containing demographic and medical information, retinal images (CFP, FAF, FA, ICG, OCT-A, SD-OCT), and the results of any other tests or assessments. All information on eCRFs must be traceable to these source documents in the patient's file. The investigator must also keep the original ICF signed by the patient (a signed copy is given to the patient).

The investigator must give the monitor access to all relevant source documents to confirm their consistency with the data capture and/or data entry. Novartis monitoring standards require full verification for the presence of informed consent, adherence to the inclusion/exclusion criteria, documentation of SAEs, and of data that will be used for all primary variables. Additional checks of the consistency of the source data with the eCRFs are performed according to the study-specific monitoring plan. No information in source documents about the identity of the patients will be disclosed.

## 12 Data analysis and statistical methods

The primary efficacy and safety analysis will be based on the Week 12 data, i.e. data up to and including Week 12. This analysis will be performed once all patients have completed their Week 12 visit or prematurely discontinued the study before/on their Week 12 visit, while patients will continue to receive study treatment until their Week 40/Week 44 visit, dependent on their treatment regimen. The analysis of the data after the EOS/Week 48 visit will be performed once all patients have completed or prematurely discontinued the study.

The data will be analyzed by Novartis and/or a designated CRO. Any data analysis carried out independently by the investigator should be submitted to Novartis before publication or presentation.

It is planned that the data from all centers that participate in this protocol will be pooled, so that an adequate number of patients will be available for analysis.

In addition to the statistical methods outlined below, further details will be described in the Statistical Analysis Plan (SAP).

### 12.1 Analysis sets

The Enrolled Set (ENS) includes all patients who signed an ICF and are assigned patient numbers.

The Full Analysis Set (FAS) comprises all patients to whom study treatment has been assigned and who received at least one IVT injection of study treatment.

The Safety Set includes all patients who received at least one IVT injection of study treatment.

The Per-Protocol Set (PPS) is a subset of patients of the FAS without PDs with impact. The list of PD criteria will be provided in a separate document.

However, when assessing the robustness of the overall efficacy conclusions, considerations will be given to the analysis based on the estimand using FAS and PPS. Expectation of comparing of both estimands is to have similar conclusions. Inconsistencies in the results will be examined and discussed in the Clinical Study Report (CSR).

### 12.2 Patient demographics and other baseline characteristics

Demographic and other Baseline data including disease characteristics will be listed and summarized descriptively for the FAS.

Categorical data will be presented as frequencies and percentages. For continuous data, mean, standard deviation, median, minimum, and maximum will be presented. For selected parameters, 25th and 75th percentiles will also be presented.

The last available assessment taken prior to the first IVT injection of study treatment is taken as the “Baseline” assessment.

Relevant medical histories and current medical conditions at Baseline will be listed.

## **12.3 Treatments**

The Safety set will be used for the analyses below. Categorical data will be summarized as frequencies and percentages. For continuous data, mean, standard deviation, median, 25th and 75th percentiles, minimum, and maximum will be presented.

The extent of exposure to study treatment as the number of IVT injections received from Baseline to the end of the treatment period will be descriptively summarized. In addition, the number of patients at each injection category (1 injection, 2 injections up to the maximum number of injections) from Baseline to the end of the treatment period will be presented.

Prior medications are defined as treatments taken and stopped prior to first IVT injection. Any medication given at least once between the day of first IVT injection and the date of the last study visit will be a concomitant medication, including those which were started pre-Baseline and continued into the period where study treatment is administered.

Concomitant medications and significant non-drug therapies prior to and after the start of the study treatment will be listed according to the Anatomical Therapeutic Chemical (ATC) classification system.

Anti-VEGF medications (other than the study treatment) will be summarized separately.

## **12.4 Analysis of the primary endpoint**

### **12.4.1 Definition of primary endpoint**

The primary endpoint is the percentage change in CNV lesion area measured by OCT-A from Baseline to Week 12. This analysis will focus on the study eye only.

The analysis of the primary variable will be based on the following estimand:

- Analysis set: FAS
- Variable of interest: Percentage change from Baseline in CNV lesion area measured by OCT-A to Week 12
- Intervention effects: Effect at Week 12, while on study treatment
- Intercurrent events: Discontinuing study treatment; treatment interruption
- Measure of intervention effect: Difference from Baseline in variable means

### **12.4.2 Statistical model, hypothesis, and method of analysis**

Descriptive statistics for the primary endpoint (actual value, change from Baseline, percentage change from Baseline) will be presented based on observed data using the FAS. Furthermore a two-sided 95% CI using Student's t-distribution will also be provided.

### **12.4.3 Handling of missing values/censoring/discontinuations**

For patients who:

- Discontinue study treatment but continue in the study, the efficacy data will be censored at the time the patient stopped study treatment in the study eye.
- Interrupt treatment, the efficacy data will be censored at the time the study treatment was first interrupted.

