## 9 Study discontinuation and completion

### 9.1 Discontinuation

#### 9.1.1 Discontinuation of study treatment

Discontinuation of study treatment for a patient occurs when study treatment is stopped earlier than the protocol planned duration, and can be initiated by either the patient or the investigator.

The investigator must discontinue study treatment for a given patient if he/she believes that continuation would negatively impact the patient's well-being.

The investigator and/or referring physician will recommend the appropriate follow-up medical care, if needed, for all patients who are prematurely withdrawn from the study.

Study treatment must be discontinued under the following circumstances:

- Patient requires treatment on a q4w interval after the initiation phase, i.e., after the three monthly injections at Baseline, Week 4, and Week 8, followed by the first interval extension
- Patient develops intraocular inflammation, including retinal vasculitis and/or retinal vascular occlusion
- Patient/guardian decision
- Pregnancy
- Use of prohibited treatment
- Any situation in which study participation might result in a safety risk to the patient

If premature discontinuation of study treatment occurs, the following should be done as appropriate:

- The investigator should make a reasonable effort to understand and document the primary reason for the patient's premature discontinuation of study treatment using the appropriate eCRF page.
- Patients who prematurely discontinue study treatment for any reason should return 4 weeks after last study treatment to perform the assessments for early treatment discontinuation (ETD). Please refer to [Table 8-1](#), except for patients who withdraw their consent from the study and do not wish to do so (refer to [Section 9.1.2](#)).
- After these assessments are performed, patient can be switched to standard of care (SOC) anti-VEGF IVT as per investigators discretion. IVT injection is contraindicated in patients with active intraocular or periocular infections and in patients with active intraocular inflammation; therefore, the investigators must verify that these conditions are not present in the study eye prior to every injection.
- After premature study treatment discontinuation, at a minimum till week 48, in abbreviated visits, the following data should be collected at clinic visits or via telephone/email contact:
  - New/concomitant treatments

- Adverse events/Serious Adverse Events
- BCVA

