Change from Baseline: The difference of measure between post-baseline and Baseline is called change from Baseline.

Percent change from Baseline: The percent change from Baseline will be calculated as below: ((post-baseline value – Baseline value) /Baseline value)*100.

On-treatment period: The on-treatment period lasts from the date of first administration of study treatment to 28 days after the date of the last actual administration of any study treatment.

Treatment duration: The maximum planned duration of treatment for each patient is 40 to 44 weeks in accordance with the designated treatment regimen. Discontinuation of study treatment for a patient occurs when study treatment is stopped earlier than the protocol planned duration and can be initiated by either the patient or the investigator.

Treatment discontinuation: When patients discontinue study treatment but continue in the study, the efficacy data will be used at the time the patient stopped study treatment.

Dry retina: Absence of fluid (IRF/SRF/sub-RPE) will be considered as dry retina.

Event for maintenance q12w interval: In case the investigator selects q12w interval for a patient and the patient maintains the q12w interval until the first q8w interval has started then this will be considered as an event. In case the investigator maintains q12w interval (does not select q8w interval at any time in study) until EOS or patients got early discontinuation from study then patients will be considered as censored.

Event for no disease activity: When patients will be with no disease status as per investigator decision after last dose in initiation phase then the patients will consider as event for disease activity. If patients with active disease status or early discontinue then patients will be considered as censored for disease activity.

Event for dry retina: When patients have absence of fluid then it will be considered as an event of dry retina. If patients have a presence of fluid before/at EOS or early discontinuation then will be censored.

Maximum duration of dry retina: The longest consecutive interval of dryness will be considered as maximum duration of dryness. This duration will be obtained from end date of dryness and start date of dryness for longest interval. If subjects obtain dryness at end of study then duration will be obtained from end of treatment.

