2.1.2 Visit windows for data analysis

Visit windows will be used for the data analysis, as per the planned visits in the protocol. During the q12w/q8w phase, i.e., from Week 16 to Week 44, the treatment visit intervals will be determined by the investigator, based on the patient's disease activity.

Table 2-1 Assessment windows for scheduled visits

Analysis Visit	Week	Scheduled Day	Visit Window
Screening/Baseline	BL	1	-14 days to Day 1*
Week 4	4	28	Day 22 - 34
Week 8	8	56	Day 50 – 62
Week 12	12	84	Day 71 – 97
Week 16	16	112	Day 99 – 119
Week 20	20	140	Day 127 – 153
Week 24	24	168	Day 155 – 182
Week 28	28	196	Day 183 – 209
Week 32	32	224	Day 211 – 237
Week 36	36	252	Day 239 – 265
Week 40	40	280	Day 267 – 293
Week 44	44	308	Day 295 – 321
Week 48	48	336	Day 323 - 349

* Baseline measurement before the first treatment administration.

If study visit assessments and the corresponding treatment occur on separate days, a repeat safety check-up should be performed prior to treatment of the eye and results documented in the source documents. If any safety concern arises related to the study eye that, in the opinion of the investigator, may be further impacted by the study treatment or injection procedure, treatment needs to be cancelled. Injections are contraindicated in patients with active intraocular or periocular infections and in patients with active intraocular inflammation; therefore, the investigators should verify that these conditions are not present in the study eye prior to every injection. Any AEs must be recorded in the eCRF.

The injection procedure for brolucizumab will be performed according to local clinical practice. Injections will be administered by the investigator.

Data collected at unscheduled visits will not be used in 'by-visit' tabulations or graphs and will be presented in listings.

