2.6.1.4 Best corrected visual acuity (BCVA)

The summary statistics (n, mean, std, median, min and max) of BCVA for nAMD patients will be presented along with change and percentage change from Baseline in BCVA by visit. Along with below BCVA category.

- 1. BCVA (≤ 55 , 56 70 and ≥ 71).
- 2. Increase of ≥ 5 , ≥ 10 and ≥ 15 letters in BCVA from Baseline up to Week 48.
- 3. Loss of ≥ 5 , ≥ 10 , ≥ 15 and ≥ 30 letters in BCVA from Baseline up to Week 48.
- 4. BCVA \geq 84.

The above analysis will be done only on the study eye. The analysis will be performed on FAS.

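### BCVA measured after treatment stop is collected to Week 48, but the censoring rule most naturally leaves it out of the all-patient vision tables, for reasons tied to outcome

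*Protocol*

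**What the plan says.** Protocol 12.4.3 gives two rules. For patients who stop treatment and stay in the study, "the efficacy data will be censored at the time the patient stopped study treatment in the study eye". For those who interrupt, "the efficacy data will be censored at the time the study treatment was first interrupted". Neither rule names an endpoint. Both sit in section 12.4 on the primary endpoint, whose estimand in 12.4.1 is "Effect at Week 12, while on study treatment" and whose only variable is lesion area.

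Two later sections reach further. Protocol 12.4.4 plans an FAS-versus-PPS comparison under the 12.4.3 censoring rules and refers to efficacy endpoints in the plural. Protocol 12.5.1 puts continuous functional outcomes, that is BCVA, through the primary analysis method.

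Protocol 9.1.1 makes stopping mandatory for IOI (including retinal vasculitis and/or occlusion) and for a need for 4-weekly injections after the initiation phase. It then says: "After premature study treatment discontinuation, at a minimum till week 48, in abbreviated visits, the following data should be collected". BCVA is one of the three items listed, and Table 8-1 marks it in the post-discontinuation column.

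SAP 2.1.1 says: "When patients discontinue study treatment but continue in the study, the efficacy data will be used at the time the patient stopped study treatment". SAP 2.6.1.4 summarises BCVA change by visit in the FAS, with letter-gain and letter-loss categories up to "≥ 30 letters in BCVA from Baseline up to Week 48". It gives no rule for stops or interruptions. SAP Amendment 2.0 and Addendum 1.0 agree on these points.

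**The concern.** BCVA is the only functional efficacy endpoint, and Protocol 4.5 names severe vision loss as a possible result of the inflammatory events. Eyes that must stop, for inflammation or because 12- or 8-weekly dosing is not enough, are those in which later vision is most in doubt. If their later BCVA is dropped, the by-visit means and the loss categories increasingly describe eyes that tolerated and responded to the drug, while still carrying an FAS label.

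Interruption widens the gap. Protocol 6.5 allows it for an adverse event or cataract surgery, and 12.4.3 makes no provision for using data again once treatment resumes.

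Nothing else in the efficacy plan fills the gap. The LOCF sensitivity analysis in SAP 2.5.1 covers lesion area only, and no BCVA analysis regardless of treatment stop is specified.

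**Working it through.** **The plan's own figure.** The only design calculation concerns lesion area: (1.96 × 35 / 5)² = 188.2, rounded up to 189, and 189 / 0.90 = 210. It reproduces. It has no bearing on BCVA except to supply the denominator of 210.

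**Does the rule reach BCVA?**
- For: 12.4.3 speaks of efficacy data without limit, 12.4.4 applies its rules to efficacy endpoints, and 12.5.1 carries the primary method to BCVA.
- Against: the rule's place in the document, an estimand that names lesion area only, and a BCVA section in the SAP with no censoring rule.
- Unclear: the SAP 2.1.1 sentence can be programmed as censoring at the stop or as carrying the stop value forward. It is also undefined whether the early-discontinuation visit, 4 weeks after the last injection, falls before or after the stop.

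The Protocol most naturally covers BCVA, but this is an inference.

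**Does SAP 2.9.1.1 close the gap?** It plans BCVA change after an adverse event of special interest (AESI) has ended, by AESI type. SAP 5.4 defines the types as IOI and retinal vasculitis/occlusion. Four limits remain:
1. It needs an event end date, so unresolved events can be missed.
2. AESI summaries take only events that start on treatment, which ends 30 days (Protocol 12.5.2) or 28 days (SAP 2.1.1) after the last injection. Injection visits are 8 × 7 = 56 or 12 × 7 = 84 days apart, so an event can start outside that period.
3. Eyes stopped for a need for 4-weekly injections are not in it.
4. It gives no mean or loss rate for the whole FAS.

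**Size in the mean.** Let m be the mean change in continuing eyes, f the share of FAS eyes stopped, and d how many letters worse the stopped eyes do. The all-eyes mean is (1 − f)m + f(m − d) = m − fd, so the censored table is too high by f × d. This applies at visits after the stops, so it is largest late in the study. The documents give no d and no overall stop rate. Protocol 4.5 gives IOI rates of 3.2% in men and 5.3% in women from the pivotal trials, without a time frame. The range d = 5 to 20 letters is assumed.

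| f | Eyes of 210 | f × d at d = 5 | f × d at d = 20 |
|---|---|---|---|
| 3.2% (documents) | 6.7 | 0.16 | 0.64 |
| 5.3% (documents) | 11.1 | 0.27 | 1.06 |
| 10% (assumed) | 21 | 0.5 | 2.0 |
| 20% (assumed) | 42 | 1.0 | 4.0 |

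**Size in the loss rate.** Assume a loss of ≥ 15 letters in 3% of continuing eyes and in 20% to 40% of stopped eyes. At f = 10%, the all-eyes rate is 0.9 × 3% + 0.1 × 20% = 4.7%, up to 0.9 × 3% + 0.1 × 40% = 6.7%. The censored table would show 3.0%. At the IOI rates, the all-eyes rate is 3.5% (f = 3.2%, 20%) to 5.0% (f = 5.3%, 40%).

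**The case against.** The strongest reply is that the censoring rule belongs to the primary endpoint. Section 12.5.1 imports a method of analysis, which is section 12.4.2 (descriptive statistics and a t-interval), and not the missing-data rule. The comparison in 12.4.4 is only one that may be done. This stands far enough that coverage of BCVA cannot be called certain. It does not remove the need to act, because two programmers could build different BCVA tables from the present texts.

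A while-on-treatment summary is also legitimate: after a switch, BCVA partly reflects another drug. That supports keeping such a table, but not having it as the only one.

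Several stronger readings are tempting, and the documents do not support them:
- A reader might infer that eyes with inflammation, vasculitis or occlusion vanish from all vision tables. Their visits before the stop remain, and SAP 2.9.1.1 summarises many of them afterwards.
- A reader might infer that severe losses in these eyes would show as near zero. A loss recorded at or before the stop can still count.
- Protocol 10.1.2 says "nAMD recurrences and their clinical manifestations are exempt from reporting", so a reader might infer that vision loss from poor response appears nowhere else. Disease activity is tabulated by visit (SAP 2.6.1.6), and reasons for discontinuation are summarised (SAP 2.3.1, 2.4.1).
- SAP 2.1.2 begins a sentence "Data collected at unscheduled visits will not be used in" and goes on to by-visit outputs. A reader might infer that it removes every visit after discontinuation. Table 8-1 gives those visits their own column, so the status is undefined rather than settled.
- A reader might take the upper illustrations as expected. Protocol 4.5 reports that over 90% of IOI events were mild to moderate and that 79% resolved without sequelae, which points to the lower part of the range for IOI alone.

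**Conclusion.** The point holds in this form. The Protocol's censoring rule most naturally takes post-stop and post-interruption BCVA out of the all-patient tables, the stopping reasons are related to outcome, and the data are meant to be collected. Mean change is therefore likely overstated and letter-loss rates likely understated.

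The size is unknown. The illustration is 0.2 to 1.1 letters at the documents' IOI rates, and 0.5 to 4.0 letters if 10% to 20% of eyes stop. Both ranges rest on the assumption that stopped eyes do 5 to 20 letters worse. The direction is plausible but not shown, since eyes switched to standard care could recover.

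The primary endpoint is not at issue. The study is single-arm and descriptive and BCVA is secondary, so this should be fixed but does not undermine the main result.

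**What to change.** - **Protocol 12.4.3:** state that the censoring rule applies to the lesion-area/OCT while-on-treatment estimand. Align SAP 2.1.1 with it, and say whether the early-discontinuation visit counts as on treatment.
- **SAP 2.6.1.4:** add by-visit BCVA change and the ≥ 5/10/15/30-letter loss categories, plus worst post-Baseline loss, for all FAS eyes. Use every clinic-measured ETDRS score regardless of stop, interruption or switch. Map visits after early discontinuation to the analysis windows and show the number with data at each visit. Keep the while-on-treatment table beside it, labelled as such.
- **Protocol 9.1.1:** make clear that telephone or email contact is not a source of ETDRS BCVA. As written it covers all three listed items, while 8.3.3 requires chart testing from an initial 4 metres.

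The cost is wording and one or two extra tables. Vision results may look slightly less favourable, and BCVA after a switch will partly reflect other treatment. Week 48 values will be incomplete, because Protocol 9.1.1 and the Table 8-1 footnotes waive attendance after early discontinuation. SAP wording alone cannot supply those values.
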